##### **1.4.4.2 Dorsum of hands**

Whilst affording effective temporization of the debrided burn wound, application of BTM on the dorsum of hands and fingers delays early mobilization of the fingers in order to allow the BTM to adhere. The thickness of the integrated BTM in its current form may also reduce the elasticity of the reconstructed skin. These properties may reduce resultant active and passive range of motion of the fingers, which can eventually be improved in the compliant and motivated patient, however primary split skin grafting to these areas would enable earlier return to motion exercises. At this time, BTM use in the dorsum of the hands is cautioned.

#### **1.4.4.3 Dorsum of feet**

The experience to date in patients with burns to the dorsum of the feet (2 feet, one patient, 6 months follow up) is that BTM facilitates effective temporization and robust cover over the extensor tendons (paratenon preserved) with good functional outcome to date.

#### **1.4.4.4 Face**

No BTM to date has been used to primarily temporize and reconstruct the face. Like the glabrous skin, limited areas of deeper burns can epithelialize effectively with conservative measures (soft paraffin application) due to the high vascularity and presence of skin appendages (glands, hair follicles). There may be a role for secondary scar revision or contracture release with BTM, however, like the dorsum of the hands, the current 2 mm thick iteration may be too thick to offer optimal results and its potential effect on the position of sensitively functional structures such as the eyelids and the oral margin is unknown and may be detrimental (causing ectropion, poor oral mobility/competence etc). At this time, BTM use in the face is cautioned.

#### **1.4.4.5 The Neck**

To date, one patient has received BTM in the neck for early secondary contracture release in burns. The initial results are encouraging but medium to long term results are unknown. The use of BTM in the neck for primary burns reconstruction is therefore cautioned.

#### **1.4.4.6 Perineum**

To date, the BTM has been applied successfully to the buttocks and the thighs. It has not been applied to the perineum or the genital area, therefore the results are not known. The use of BTM in the perineum is therefore cautioned.

### **1.4.5 Potential Benefits**

For moderate to large burn injuries in subjects, grafting at a second operation allows significant physiological recovery of the subject prior to graft harvest and application. Reducing the early surgical 'insult' to major burn injury sufferers is important in assisting patient survival and reduces the risk of loss of resources (such as harvested applied skin

grafts and skin graft donor sites) secondary to physiological insufficiency or deterioration. The cosmetic and functional outcomes of using commercially available dermal matrices before grafting are considerably better than a SSG alone, however their composition (collagen/other biological materials) may increase the risk of infection. Given the potential for increased susceptibility to infection and the high cost of existing matrix products, their use is typically restricted to burns >50% of TBSA. The benefits of BTM may include improvements in skin function and cosmesis, and with a much more cost-effective material and strategy than standard dermal matrices.

#### **1.4.6 Warnings**

The following complications are possible with the use of BTM. If any of the following conditions occur, the device should be removed: chronic inflammation, allergic reaction, excessive redness, pain or swelling.

BTM should only be applied onto surgically debrided wounds where underlying pathology capable of potentiating the wound has been addressed (e.g. meticulous blood sugar control in diabetic ulceration, compression hosiery/dressings in venous ulceration to combat sustained venous hypertension, etc.). BTM should be applied onto wounds only after effective haemostasis has been afforded.

## 2 OBJECTIVES

### 2.1 Study Objectives

The purpose of the trial is to evaluate the safety and effectiveness of the ability of the BTM class III medical device to satisfactorily fulfill the trial endpoints and thus evaluate the appropriateness and applicability of those endpoints for the subsequent pivotal trial. Within the confines of the trial, biodegradable polyurethane will become incorporated into the subjects' wounds to form a neo-dermis. Specifically, temporization of the wound (prevention of contraction and infection), integration and ability to sustain split skin graft 'take' will be evaluated.

#### **Primary Objectives:**

The primary objectives of this clinical trial are:

- To obtain preliminary data on the clinical safety and effectiveness of BTM.
- To assess the %BTM 'take' rate (%TBSA of BTM that has adhered at time of skin grafting, divided by the %TBSA treated with BTM, then multiplied by 100 to express as a percentage).
- To assess the %SSG (Split Skin Graft) 'take' rate (%TBSA of viable skin graft (taken) at day 7 - 10 post-SSG, divided by the %TBSA of SSG applied, then multiplied by 100 to express as a percentage).

#### **Secondary Objectives:**

The secondary objectives of this clinical trial are:

- To assess the incidence and severity of infections in BTM-treated burn wounds.
- To assess % wound closure in BTM-treated burn wounds.
- To assess the appropriateness of the study endpoints and the study design, including operator ease of use and subject characteristics that may reflect the impact of the device performance.
- To assess the quality of wound healing in subjects treated with BTM, using Joint Contracture Severity Scale, measurements of the Range of Motion (ROM), and scar appearance/quality scales using the modified Vancouver Scar Scale (mVSS) (Appendix 2).

- To assess the incidence and severity of pruritus as assessed by Numerical Rating Scale (NRS) (Appendix 2).

## 2.2 Study Outcomes Measures

### Primary Endpoints:

- Incidence and type of adverse events occurring after BTM implantation. This will also be reviewed by a Data Safety Monitoring Board (DSMB).
- BTM 'take' rate. Amount of BTM that is viable (taken) at the time of skin grafting, expressed as a percentage of the total amount of BTM applied.
- SSG 'take' rate. Applied skin graft which remains viable ('takes') expressed as a percentage of the total amount of SSG applied 7 -10 days after application of the SSG.

### Secondary/Exploratory Endpoints:

- Incidence and severity of infections at the wound site, and the success of treatment of local infections with BTM in place.
- Clinical assessment of % wound closure.
- Operator ease of use as determined by the physician survey (Appendix 2).
- Joint contracture at 1, 2, 3, 6 and 12 months after treatment compared with baseline. This will be assessed by Joint Contracture Severity Scale and Range of Motion (ROM) of joints (Appendix 2).
- Scar appearance/quality in BTM -treated wounds as assessed by Modified Vancouver Scar Scale (mVSS) (Appendix 2) at 2, 3, 6 and 12 months after SSG.
- Pruritus incidence and severity as assessed by NRS at SSG 'take' and 1, 2, 3, 6 and 12 months after SSG.

## 3 STUDY DESIGN

### 3.1 Study Population

The study population includes severely ill subjects who have sustained life threatening deep burn injuries and who would usually receive Integra® dermal regeneration template, a similar dermal matrix, xenograft or cadaver allograft, to facilitate functional healing (i.e. those subjects with >10% TBSA full thickness burn injuries). However, beyond the upper end of this range (>70% TBSA full thickness burns), subjects with such injuries experience high subject mortality so that their inclusion in such a trial is not deemed prudent. Instead, this trial aims to recruit a minimum of ten subjects and a maximum of up to 15 subjects suffering deep-dermal or full thickness burn injuries to between 10% and 70% TBSA and who are able to provide informed consent, or have a legal representative who is able to make medical decisions on behalf of the subject.

### 3.2 Study Design Rationale

The proposed trial is a traditional feasibility trial to assess the appropriateness and applicability of the proposed BTM device outcomes and the measurement of those outcomes for use in a subsequent pivotal trial. Since outcomes for standard of care are defined at each study site, there is no plan to assess those standards of care or their outcomes in this trial design.

### 3.3 Trial Sites

The intention of this multicenter (up to 6 US sites) trial is to provide data for a feasibility assessment of the BTM medical device.

### 3.4 Treatment Group(s)

This will be a single-arm study with all feasibility trial subjects receiving BTM. A minimum of ten (10) subjects will be recruited.

### 3.5 Recruitment Period

Six (6) months

### **3.6 Duration of Subject Participation**

Study participation will last approximately 14 months, divided into an acute care period and a rehabilitation/therapy period.

- **Screening:** approximately 1-2 days (within Day -7 to Day 0)
- **Treatment:** approximately 2 months (from admission to hospital through to the end of graft 'take')
- **Follow-up:** 12 months

### **3.7 Outcomes**

Three primary and seven secondary outcomes have been chosen for this study, with a view to providing both subjective and objective clinical measures/data to demonstrate safety and effectiveness of BTM, as well as, the appropriateness and applicability of both the outcomes and the methods by which they are measured.

### **3.8 Safety oversight**

An independent DSMB will be established to ensure unbiased oversight of the traditional feasibility trial.

## 4 STUDY ENROLLMENT AND WITHDRAWAL

### 4.1 Subject Inclusion Criteria

Subjects must fulfill **all** of the following inclusion criteria to be eligible to participate in the study:

1. Provides written informed consent (directly or via legal representative) prior to any clinical trial procedures being performed.
2. Willing to comply with all study procedures and expects to be available for the duration of the study.
3. Male and females  $\geq 18$  years of age and  $\leq 70$  years of age.
4. Patients with deep partial or full thickness burns (between 10% and 70% inclusive of their TBSA). The %TBSA will be determined using the rule of nines. For small areas within a particular anatomic region (as defined by the rule of nines), the rule of the palm may be used. Note: The electronic case report form (eCRF) and eCRF completion guidelines detail the localization of each burn region and corresponding wound size with % TBSA.
5. Females, who are non-pregnant (i.e., has a negative urine human chorionic gonadotropin [ $\beta$ -hCG] pregnancy test at Day 0, prior to BTM being applied), non-lactating, or are naturally postmenopausal (i.e.,  $\geq 12$  months of natural spontaneous amenorrhea), surgically sterile, or who agrees to use effective contraceptive methods throughout the course of the study. Effective contraceptive is defined as:
  - Surgically sterile (bilateral tubal ligation with surgery at least 6 weeks prior to screening, hysterectomy, or bilateral oophorectomy)
  - Intrauterine device (IUD) in place for at least 3 months prior to use of study device
  - Abstinence (not having sexual intercourse)
  - Barrier method (condom or diaphragm) with spermicide for at least 14 days prior to screening and through study completion
  - Stable hormonal contraceptive for at least 3 months prior to study and through study completion

### 4.2 Subject Exclusion Criteria

Subjects will **not** be included if any one or more of the following conditions exists:

1. Has a known hypersensitivity to polyurethane or silver-containing materials.
2. Multiple traumas (i.e. significant traumatic injury to a solid organ in addition to skin).

3. Presence of a medical condition with a life expectancy of less than 12 months, such as advanced malignancy.
4. Presence of a medical condition that might interfere with treatment evaluation; or require a change in therapy including but not limited to, significant immune deficiency, or skin or vascular diseases in the area of the wound.
5. Has known or suspected pregnancy, planned pregnancy, or lactation (for female subjects).
6. Has exposure to any other investigational agent within the last 6 months.
7. Has clinically significant psychiatric illness (as determined by the Investigator).
8. Has a condition the Investigator believes would interfere with the ability to comply with study instructions, or that might confound the interpretation of the study results or put the subject at undue risk.

#### **4.3 Strategies for Recruitment and Retention**

Subjects will be recruited into the clinical trial through the Investigator's burn unit. Subjects may be compensated for their participation as described in the Informed Consent Form (ICF). Once discharged from the burn unit, subjects will be contacted as part of the standard of care (monthly at a minimum) by the investigational site staff to remind them of follow-up visits and ensuring trial compliance.

If the recruitment rate is found to be insufficient, additional sites may be added to increase the rate.

#### **4.4 Enrollment**

After burn size, depth assessment and formulation of the immediate surgical plan, the subject/or legal representative will be informed about the trial. After provision of, and the opportunity of the subject/legal representative to read, and understand, a study information sheet, and after the subject/legal representative has been allowed to ask any questions of the Investigator, signed consent, [photographic and standard institutional surgical consent as applicable] will be obtained following reiteration of the trial details. The subject will then be screened for inclusion/exclusion criteria. If all criteria are met, the subject will be enrolled into the trial.

#### **4.5 Subject Withdrawal**

Subjects may withdraw voluntarily from the trial at any time without penalty or impact on their treatment or the Investigator or PolyNovo may terminate a subject's participation.

#### **4.5.1 Reasons for Withdrawal**

Subjects are free to withdraw from participation in the trial at any time upon request.

An Investigator or PolyNovo may terminate a subject's participation in the trial if:

- Any clinical adverse event (AE), laboratory abnormality, or other medical condition or situation occurs such that continued participation in the trial would not be in the best interest of the subject.
- The subject meets an exclusion criterion (either newly developed or not previously recognized) that precludes further participation.
- Inability or unwillingness to complete the trial or subject noncompliance.
- Adverse event, which is directly attributed to the presence of the implant, where there is no other explanation for the effect.

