#### **4.5.2 Handling of Subject Withdrawals or Subject Discontinuation of the Investigational Device**

Subjects withdrawn early due to an AE will be followed until medically stable or resolution of the AE.

If withdrawal from the study is requested by the subject, prior to BTM integration (i.e. **before Day 7** post-implantation), the BTM device can be removed and the wound bed closed by the application of an autologous SSG. However, **≥ Day 7** the BTM can be removed, but it is **not recommended**, as integration will likely have occurred to a point such that BTM removal would result in damage to the subject's burn wound. In either case, no data or BTM -related follow-up will be imposed. Physicians are expected to follow subjects according to their institution's standard of care. Investigational Device Exemption (IDE) regulations require investigators to maintain each subject's case history and exposure to the device.

All consented subjects who have been implanted with BTM, even in the event of device failure, will have all lesions followed up as a part of the study until completion or if/when withdrawal from the study is requested by the subject.

If subjects do not complete 3 months follow up **post SSG** implantation for any reason, they will be replaced with further subjects that meet the inclusion/exclusion criteria, to

ensure that the final cohort is (a minimum of) 10 subjects.

In case of withdrawal, the Investigator will promptly inform the Institutional Review Board (IRB) within 5 working days and will provide the reason(s) for the withdrawal. All applicable source documentation will be collected to confirm resolution.

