## 8 ASSESSMENT OF SAFETY

Subjects will be monitored throughout the clinical trial for adverse events/effects. Subjects will be instructed on the need to inform the Investigator and/or clinical trial staff of any AEs that may occur at any time during the clinical trial.

Adverse events considered related to the investigational device (ID), as judged by a medically qualified Investigator or PolyNovo, will be followed either until resolution or the event is considered medically stable.

It will be left to the Investigator's clinical judgment to decide whether or not an AE is of sufficient severity to require the participant's removal from treatment, prior to Day 7 after BTM implantation. A participant may also voluntarily withdraw from treatment until Day 7 after BTM implantation without giving a reason. In either event, a Termination visit assessment will be performed. In the event of AE termination by the Investigator, the subject will be given appropriate medical care until symptoms cease, or until the condition becomes stable.

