### 8.1 Specification of Safety Parameters

The following information will be recorded in the eCRF for all Adverse Events: description, date/time of onset and end date, severity, assessment of relatedness to the ID, other suspect drug or device, and action taken. Follow-up information should be provided until resolution or as appropriately deemed by the Investigator.

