2.3. Overall Study Design and Plan

This is a multicenter, single arm, open-label study to allow a preliminary assessment of the safety and effectiveness of BTM device. Patients with 10-70% TBSA burns will have BTM devices implanted in areas with deep partial or full thickness burns to treat at least 5% and no more than 50%TBSA.

This trial aims to recruit a minimum of ten subjects and up to 15 subjects suffering deep-dermal or full thickness burn injuries to between 10% and 70% TBSA and who are able to provide informed consent, or have a legal representative who is able to make medical decisions on behalf of the subject.

The study will consist of approximately a 1-2 day screening period, a 2 month treatment period, and a 12 months follow-up period. The screening period will start from the day of signing the Informed Consent Form until Day 0 of treatment within 7 days. The treatment period will last approximately 2 months starting from admission to hospital through to the end of graft 'take'. The follow-up period will start from the day after the end of graft take date.

There is no restriction on administration to the subject of their usual medication, or such pharmaceutical treatments felt necessary by the Investigator such as antibiotics or topical aqueous only antimicrobial solutions.

Subjects will be monitored throughout the clinical trial for adverse events/effects. It will be left to the Investigator's clinical judgment to decide whether or not an AE is of sufficient severity to require the participant's removal from the trial, prior to Day 7 after BTM implantation. A participant may also voluntarily withdraw from follow-up treatment after BTM implantation without giving a reason. In either event, a Termination visit assessment will be performed. In the event of AE termination by the Investigator, the subject will be given appropriate medical care until symptoms cease, or until the condition becomes stable.

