8.1.5. Adverse Events Leading to Early Termination

It will be left to the Investigator’s clinical judgment to decide whether or not an AE is of sufficient severity to require the participant’s removal from treatment, prior to Day 7 after BTM implantation.

All AEs including UADEs leading subject to study discontinuation will be presented in a listing.

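### Protocol 4.5.1 lets the investigator or sponsor end trial participation for a device-caused adverse event, while 4.5.2 requires follow-up of every implanted subject; the two must be reconciled

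*Protocol*

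**What the plan says.** Protocol 4.5.1 opens its list of termination grounds with "An Investigator or PolyNovo may terminate a subject's participation in the trial if". The first bullet covers adverse events, laboratory abnormalities and other conditions, but only where staying in the trial would not be in the subject's best interest. The fourth bullet reads "Adverse event, which is directly attributed to the presence of the implant, where there is no other explanation for the effect" and has no such condition.

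Protocol 4.5.2 states "All consented subjects who have been implanted with BTM, even in the event of device failure, will have all lesions followed up" as part of the study, and names two end points: completion, or withdrawal requested by the subject. The same section says "Subjects withdrawn early due to an AE will be followed until medically stable or resolution of the AE", and provides that a subject who does not complete 3 months post graft, whatever the reason, is replaced so that the final cohort has at least 10.

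On early removal for an adverse event, Protocol 8 leaves to the investigator's judgment "removal from treatment, prior to Day 7 after BTM implantation". SAP 2.3 has the corresponding sentence as "removal from the trial, prior to Day 7 after BTM implantation". SAP 8.1.5 opens with the treatment wording but then provides only this output: "All AEs including UADEs leading subject to study discontinuation will be presented in a listing".

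**The concern.** Stopping the device and leaving the study are different events, and these sections do not keep them apart consistently. Under 4.5.1 a subject can leave scheduled follow-up because the device caused harm, so observation would stop for a reason tied to the outcome under study. Adverse events after implantation are a primary endpoint. Contracture, scar, itch and closure over the 12 months after grafting are secondary endpoints, and the results are meant to guide a pivotal trial. With 10 to 15 subjects, one or two such exits could matter to a descriptive summary.

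The concern is with termination by the investigator or sponsor. The subject's right to withdraw is not in question.

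**Working it through.** The plan states no hypothesis and makes no formal sample size calculation, so there is no planned figure to reproduce. The check sets the sections side by side.

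1. **What the fourth bullet adds.** An adverse event that makes continued participation contrary to the subject's interest already falls under the first bullet of 4.5.1. The fourth bullet therefore adds only device-caused events where continuing would not be against that interest.

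2. **The conflict.** Take an implanted subject with an event attributed solely to the implant who has not asked to leave. Protocol 4.5.1 permits termination. Protocol 4.5.2 requires follow-up to completion and names no exit by decision of the investigator or sponsor. Neither section says which prevails.

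3. **Scope and timing of removal for an adverse event.**

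| Place | Removal from | Time limit |
|---|---|---|
| Protocol 4.5.1, fourth bullet | trial participation | none |
| Protocol 8 | treatment | before Day 7 |
| SAP 2.3 | trial | before Day 7 |
| SAP 8.1.5, opening sentence | treatment | before Day 7 |
| SAP 8.1.5, listing | study | none |

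4. **What is kept after termination.** The Early Termination visit (Protocol 6.8) records contracture and range of motion, closure, mVSS, NRS, infection, adverse events and photographs. The event that led to withdrawal is followed to stability or resolution (4.5.2). New adverse events are recorded for 7 days, and serious ones for 30 days, after the last day of participation (8.2).

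5. **What is lost.** Scheduled in-person follow-up falls at 1, 2, 3, 6 and 12 months post graft, which is 5 visits. Two assumed cases show how far the loss depends on the timing left open in step 3:
   - Termination just after the 1-month visit (possible only if no Day 7 limit applies): 5 − 1 = 4 scheduled visits and 12 − 1 = 11 months are lost.
   - Termination before Day 7: all 5 visits are lost. Both take rates are also missing, because Appendix 1 schedules BTM take only at Visit 4 and graft take only at Visit 5, and neither appears in the termination column.

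6. **Replacement.** With at most 15 enrolled and 10 needed at 3 months, there is room for 15 − 10 = 5 replacements, or 5/15 = 33%. That is a ceiling for early exits of every kind. No dropout rate or split by reason is given, so the number due to device-caused termination could be anything from 0 to 5.

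7. **Reporting of device loss.** The plan foresees it: Protocol 1.4.6 lists conditions for removing the device, and 7.2 says a haematoma may lead to replacement of a section. Protocol 8.1 records for every adverse event the "assessment of relatedness to the ID, other suspect drug or device, and action taken". Yet the SAP 8.1 overview has categories for any event, serious events, device-related events, early termination and death, with none for removal or replacement of BTM. SAP 6.2.1 and 6.2.2 plan no exposure, compliance or modification analysis. For a subject kept on study under 4.5.2 after losing BTM to an adverse event, no specified category marks that event as the cause of the loss.

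**The case against.** The strongest reply is that little is hidden:

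- ITT is everyone treated with BTM (SAP 3.3.2), so a terminated and replaced subject stays in the analysis.
- Reasons for discontinuation are tabulated (SAP 4.1). Events leading to termination are counted in the overview and listed (SAP 8.1, 8.1.5).
- The DSMB reviews all subjects (SAP 3.4).
- The default denominator is the analysis population, with a row for missing data where needed (SAP 3).
- The contracture tables are joint-level shifts, one of them to the worst post-baseline value (SAP 7.2.3), so contracture present at the termination visit can still count.
- Three places put adverse-event removal before Day 7, so late termination is only one reading.
- The heading of 4.5.2 itself separates withdrawal from discontinuing the device.

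All of this stands, and it rules out two stronger readings that a reader might infer. One is that terminated subjects vanish and every later table is biased. The documents do not support that: no completers-only set is defined, and data up to and including the termination visit are retained. The other is that losing the device to an adverse event would go unseen. BTM area not adhered at grafting lowers the take rate, device-related events are summarised, and the SAP does not fix the listing columns, so the action-taken field may well be shown.

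What the reply does not remove is the contradiction itself, the loss of scheduled data after termination, and the absence of any SAP rule for take rate, closure, mVSS, NRS or contracture values missing for that reason beyond a row for missing counts.

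**Conclusion.** The point holds as an internal contradiction with a limited consequence. Protocol 4.5.1 and 4.5.2 cannot both be followed. Protocol 8, SAP 2.3 and SAP 8.1.5 add a second disagreement, on treatment versus trial and on whether Day 7 is a limit. If 4.5.1 is applied, the result is selective missing data after the Early Termination visit.

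The size cannot be derived. It depends on how many subjects are terminated on this ground, when, and whether their later outcomes would have been worse than those of subjects who remain; the documents give none of these. A shift toward a favourable picture is plausible if device-caused harm goes with poorer later healing, but that is an assumption. The change is worth making because it is cheap and the cohort is small.

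**What to change.** 1. Reconcile Protocol 4.5.1 with 4.5.2 so that a device-attributed adverse event is not in itself a ground for ending scheduled study follow-up of an implanted subject. Leave the best-interest ground in the first bullet and the subject's right to withdraw as they are.
2. Reconcile Protocol 4.5.1, Protocol 8, SAP 2.3 and SAP 8.1.5 on removal from treatment versus removal from the trial, and on the Day 7 limit. Which clinical rule applies is for the sponsor and investigators to settle; this review does not choose one.
3. In SAP 8.1 and 8.1.5, report adverse events leading to partial or complete BTM removal or replacement separately from those leading to study discontinuation, using the action-taken field already collected.

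The cost is wording in both documents, one extra row or listing, and a few already scheduled visits kept for subjects who would otherwise have been terminated. No new data field is needed.
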